#### C.5.1.4 Major Adverse Event

Major adverse event (MAE) includes:

- MACCE
- Acute kidney Injury
- Cardiac tamponade
- Prosthetic valve dysfunction
- Cardiogenic shock
- Prosthetic valve endocarditis
- Life-threatening, disabling or major bleeding
- Major vascular complication
- Cardiac perforation
- Valve malpositioning

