### *C.5.2 Reporting*

Investigators are required to keep records on “all relevant observations, including records concerning adverse device effects (whether anticipated or unanticipated)” [21 CFR 812.140; ISO 14155 (2011)]. Adverse event collection will begin from the point of trial enrollment to trial closure. All new or worsening (from baseline) adverse events and technical observations will be captured on the AE eCRF through the 24-month follow-up visit. It is the responsibility of the Investigator to assess the subject for adverse events and capture the required adverse event information on the AE eCRF.

Once a subject has completed their 24-month scheduled follow-up visit only serious adverse events, major adverse events, cardiovascular events, device-related adverse events, including device related technical observations, unanticipated adverse device effects (UADE) or unanticipated serious adverse device effects (USADE), all strokes (CVAs) and deaths will be required to be reported. Reference section C.5.1 Adverse Events for event definitions and criteria. Medtronic representatives or their designees will conduct monitoring visits to review source documentation and verify the complete and accurate capturing of adverse events.

The Investigator must also notify the responsible IRB/MEC regarding new and significant safety information and any event identified by Medtronic that requires expedited FDA, and/or local regulatory agency, reporting as serious, unexpected, and related to the investigational device. It is the responsibility of the investigator to ensure site specific IRB/MEC safety reporting requirements are met.

Medtronic Clinical will ensure all device-related adverse events and all procedure-related SAEs are processed according to internal policies and procedures. When necessary, Medtronic Field Assurance will respond to sites in writing with the findings related to the product experiences.

The general procedure for investigators reporting any adverse event is as follows:

- Report the event to Medtronic as soon as possible but no later than the timeframes outlined below. (At the time of Site Initiation, sites will be provided with the telephone and other applicable contact information of the appropriate Medtronic designee).
- Complete all sections of the Adverse Event eCRF.
- Each unique event/diagnosis must be documented separately.

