##### C.6.7.2 Analysis of ITT and mITT Populations

For the subjects in the randomized population the primary analysis of the primary endpoint and inferential statistics for the following secondary endpoints will be performed on the ITT and mITT populations:

- Major adverse cardiovascular and cerebrovascular events (MACCE)
- Individual MACCE components
- Major adverse events (MAE)
- Conduction disturbance requiring permanent pacemaker implantation
- NYHA
- Six-minute walk test
- Ratio of days alive out of hospital versus total days alive
- Quality of life
- Echocardiographic assessment of valve performance
- Aortic valve disease-related hospitalizations
- Cardiovascular deaths and valve-related deaths
- Strokes and TIAs
- Per-procedural neurological injury

- Index procedure-related MAEs
- Length of index procedure hospital stay
- Device success
- Procedure success

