For each treatment group, the proportion of subjects with a neurologic injury (stroke, TIA, or encephalopathy) at discharge or at 7 days post-index procedure (whichever occurs first) will be calculated. The numerator will be the number of subjects with a neurologic injury (stroke, TIA, or encephalopathy) at discharge or at 7 days post-index procedure (whichever occurs first), and the denominator will be the number of subjects in that treatment group. Results will also be presented separately for disabling stroke, non-disabling stroke, TIA, and encephalopathy. Proportions will be compared between groups using Bayesian version of a comparison of proportions.

17. Index procedure related MAEs

Index procedure-related MAE events will be summarized and event rates will be provided at 30 days. The numerator will be the number of procedure-related MAE events experienced by the end of the 30-day follow-up visit, and the denominator will be the number of subjects evaluated at the 30-day follow-up visit (or a later follow-up) plus the number of subjects not evaluated but who experienced a procedure-related MAE event prior to the end of the follow-up visit window.

The endpoint is descriptive and no statistical hypothesis test will be performed.

18. Length of index procedure hospital stay

The length of TAVI or SAVR hospital stay will be summarized for all subjects undergoing a trial procedure.

The endpoint will be evaluated between groups using a Bayesian version of a t-test.

19. Presence of atrial fibrillation at post-procedure, discharge, 30 days, 6 months, 12 months, 18 months, 24 months, and annually thereafter up to 5 years.

The statistical method will be the Bayesian version of a comparison of proportions (with predictions).

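### The index-procedure MAE figure (secondary endpoint 17) divides events by subjects, so it is not the share of patients affected, and the contrast between arms can shift in either direction

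*Combined protocol and SAP*

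**What the plan says.** Item 17 of C.6.8.1 opens with "Index procedure-related MAE events will be summarized and event rates will be provided at 30 days". It then defines the two parts of the rate.

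- Numerator: "The numerator will be the number of procedure-related MAE events experienced by the end of the 30-day follow-up visit".
- Denominator: it starts as "the denominator will be the number of subjects evaluated at the 30-day follow-up visit (or a later follow-up", and the text then adds "plus the number of subjects not evaluated but who experienced a procedure-related MAE event prior to the end of the follow-up visit window".

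The item closes with "The endpoint is descriptive and no statistical hypothesis test will be performed".

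Other sections that bear on it:

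- C.5.2 (Reporting) tells sites "Each unique event/diagnosis must be documented separately".
- C.5.1.4 lists the MAE components. "Life-threatening, disabling or major bleeding" is one of them, alongside MACCE, acute kidney injury, cardiac tamponade, major vascular complication and cardiac perforation, among others.
- C.6.7.2 states that "inferential statistics for the following secondary endpoints will be performed on the ITT and mITT populations", and index procedure-related MAEs are on the list that follows.
- C.6.10.1, in its closing paragraph, allows summary data from secondary objectives outside the testing hierarchy to appear in device labelling, without any inferential claim.

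**The concern.** The numerator and denominator of item 17 are in different units. The second part of the denominator brings in unevaluated subjects who had an event. That device is used so that everyone counted on top is also counted below, which is what a proportion of subjects requires. With events on top, the construction no longer gives a proportion.

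A reader who sees a percentage labelled as a 30-day MAE rate in a table comparing TAVI with SAVR will probably take it as the share of patients who had a procedure-related MAE. Followed literally, the definition gives something larger whenever patients with any such event tend to have more than one. The figure also could not be set beside the 30-day MAE incidence in item 3, which is compared as proportions.

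What is at stake is the interpretation of one descriptive safety figure, and its possible use in labelling. The primary endpoint and the hierarchical claims are not affected.

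**Working it through.** **Plan's own figure.** The documents give no expected value for item 17, so there is nothing to reproduce. The check is of the definition, followed by algebra on assumed values.

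**Step 1: the counting rule.** Item 17 has no first-event or one-per-subject rule. Item 16, immediately before it, defines its numerator as a number of subjects. The two adjacent items therefore use different units over denominators that both count subjects.

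**Step 2: can one patient add more than one?** Yes, from the definitions alone. Take a left ventricular perforation with tamponade that needs pericardiocentesis:

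- cardiac perforation is an MAE (C.5.1.4);
- cardiac tamponade is an MAE (C.5.1.4);
- left ventricular perforation is a major vascular complication (O.2, Vascular Complications), which is an MAE;
- pericardial bleeding that needs pericardiocentesis is life-threatening bleeding (O.2, Bleeding Event), which is an MAE.

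O.2 also classes everything that happens before extubation or access-site closure as procedure-related. One complication in one patient can thus put 4 in the numerator and 1 in the denominator.

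**Step 3: formula.** For each arm let p be the share of subjects with at least one procedure-related MAE and m the mean number of such MAEs per affected subject. Then

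- reported figure = p × m;
- reported difference = pT·mT − pS·mS;
- reported ratio = (pT/pS) × (mT/mS).

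The figure equals p only if m = 1. It passes 100% when m > 1/p. At p = 25% that needs m > 4, so this is a property of the definition rather than a forecast.

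**Step 4: range for one arm (assumed p and m).** Lowest: 0.15 × 1.3 = 19.5%, against a true share of 15%. Highest: 0.25 × 2.0 = 50%, against 25%.

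**Step 5: contrast between arms (assumed p and m, TAVI / SAVR).**

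| p | m | Difference and ratio in subjects affected | p × m | Reported difference and ratio | Effect |
|---|---|---|---|---|---|
| 20% / 20% | 1.5 / 1.5 | 0; 1.00 | 30% / 30% | 0; 1.00 | unchanged |
| 20% / 30% | 1.5 / 1.5 | −10 points; 0.67 | 30% / 45% | −15 points; 0.67 | difference enlarged, ratio unchanged |
| 20% / 30% | 1.2 / 1.8 | −10 points; 0.67 | 24% / 54% | −30 points; 0.44 | enlarged |
| 20% / 30% | 1.8 / 1.2 | −10 points; 0.67 | 36% / 36% | 0; 1.00 | reduced to nothing |
| 20% / 25% | 1.8 / 1.2 | −5 points; 0.80 | 36% / 30% | +6 points; 1.20 | reversed |

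With 20% affected in both arms and m of 1.3 in one and 1.8 in the other, the arms would show 0.20 × 1.3 = 26% and 0.20 × 1.8 = 36%. That is a 10-point gap with no difference in patients affected.

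**Step 6: consistency with item 3.** Procedure-related MAEs are a subset of all MAEs. If, for example, 25% of subjects had any MAE by 30 days and 20% had a procedure-related one with m = 1.5, item 3 would show 25% and item 17 would show 0.20 × 1.5 = 30%. The subset would appear larger than the whole. These values are again assumed.

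**Step 7: inference.** If the comparison of proportions used for neighbouring endpoints were applied here, as the C.6.7.2 list could be read to require, a binomial model would not fit a count to which one subject can contribute several times.

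**The case against.** The best defence is that nothing is tested. Item 17 says so itself, and it lies outside the hierarchy in C.6.10 and C.6.10.1. That stands, and it limits the weight of the point. The list in C.6.7.2 is weak evidence of a planned test, because it also names device success and procedural success, which C.6.8.2 declares descriptive and TAVI-only. This too is fair: the two sections conflict and need reconciling, but the specific text of item 17 is the better guide to intent.

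It can also be said that events per subject over a fixed window is a legitimate summary, and that the text does speak of event rates. The first part is right. However, the denominator rule belongs to a proportion, and nothing tells the reader that the result is a mean count.

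Third, item 3 already gives subject-level MAE incidence and components at 30 days. It does, but not restricted to procedure-related events.

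Fourth, the instruction to record events separately governs site reporting rather than analysis, and C.6.5.2 refers to the SAP for further analysis details. The SAP is not in the text available here, so a counting rule there cannot be excluded. If one exists, the protocol should still agree with it.

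A reader might go further and infer that the difference between arms is overstated, or that the TAVI figure is inflated because an arterial access injury with major bleeding counts twice. The documents do not support either. The same rule applies to both arms, and the direction depends on m in each, which is nowhere given. Kidney injury, tamponade, shock and bleeding can also cluster after surgery, and the definition of a major vascular complication covers aortic dissection and rupture as well as access injury.

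**Conclusion.** The point holds in a limited form. Read literally, item 17 gives events per subject over a denominator designed for a proportion. Each arm's figure overstates the share of subjects affected by the factor m whenever m exceeds 1. No direction can be assigned to the effect on the contrast between arms.

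The mismatch of units rests on the text alone. Every percentage in the working rests on assumed values of p and m, and the real size is unknown.

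The practical consequence is small but not nil. The figure appears among endpoints compared between the arms, one section of the protocol places it under inferential statistics, and summary data of this kind may reach labelling. It is worth correcting because the correction is cheap, not because any trial conclusion depends on it.

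**What to change.** In item 17 of C.6.8.1, define the numerator as the number of subjects with at least one index procedure-related MAE by the end of the 30-day visit window. Keep the subject-level denominator as it stands; numerator and denominator then share both the unit and the cut-off. Report the total number of procedure-related MAEs on a separate line, for example per 100 subjects, labelled as a count.

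Reconcile C.6.7.2 with item 17 on whether any inference is made. If none is, take the endpoint off the inferential list. Carry the same counting rule into the SAP.

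The cost is a few sentences and no new data. Repeat events in one patient would no longer show in the headline figure, but the separate count keeps them.

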#### C.6.5.2 Randomization, Sample Size and Analysis Plan

Randomization will follow a 1:1 (treatment:control) allocation ratio and be stratified by site and need for revascularization, using a blocked randomization scheme with blocks of randomly varying sizes. The sample size for the mITT population is 1600 subjects.

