### C.6.10 Multiplicity Considerations

It is recognized that with a multiplicity of tests comes inflation in the chance of a false finding of superiority or non-inferiority. Therefore, for the purpose of seeking approved labeling claims on designated secondary objectives, the following standard will be used: If the primary objective demonstrates non-inferiority, claims will be sought for selected secondary non-inferiority and superiority objectives and for superiority on the primary objective metric. These will be tested via a hierarchical (sequential) testing order that preserves the overall study-wise type I error rate at the level of 0.05, while requiring all non-inferiority tests to meet a nominal type I error rate of 0.05 and all superiority tests to meet a nominal type I error rate of 0.025. The testing order is specified below. The following objectives are tested in order, and testing continues if and only if all previous objectives have met their designated success criterion.

1. Primary endpoint (non-inferiority)

2. Transvalvular mean gradient at 12 months (non-inferiority)
3. Effective orifice area at 12 months (non-inferiority)
4. Change in NYHA classification from baseline to 12 months (non-inferiority)
5. Change in KCCQ score from baseline to 30 days (non-inferiority)

All of the above are non-inferiority tests and are tested with a type I error standard of 0.05. If all of the above tests meet their success criterion, the type I error rate of 0.05 that is passed on from the above tests will be split equally (using a Bonferroni justification) between the following parallel subfamilies, so that each subfamily is tested using a type I error rate of 0.025:

Subfamily #1: Primary endpoint (superiority)

Subfamily #2: Secondary (superiority) objectives #5–#18 as enumerated below, tested in ordered sequence such that all  $\alpha$  is passed on to subsequent tests if a test criterion is met, while all testing stops if a test criterion is not met. This procedure controls the type I error rate of this subfamily at the level 0.025.

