It is not necessary to “pass” all objectives in one subfamily in order to test the objective(s) in the other subfamily. For the purposes of seeking claims, these objectives will only be evaluated once, at the same time as non-inferiority of the primary objective is established. The only exception to this is the primary endpoint superiority test, which carries the possibility of a delayed determination of superiority (as described in Section 4.2.1) and may thus meet its success criterion at a different time.

The remaining secondary objectives may be of interest for scientific or financial reasons but will not be the basis for supporting labeling claims; they are thus outside of the hierarchical testing procedure. Similarly, for those objectives that test non-inferiority, if non-inferiority is established, a test of superiority will also be conducted, but unless specifically itemized in the list, such superiority testing is not part of the hierarchical testing procedure; these superiority tests may be of interest for scientific or financial reasons but will not be the basis for supporting labeling claims.

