where  $\mu_{TAVI}$  and  $\mu_{SAVR}$  denote the mean improvements in the KCCQ score from baseline to 30 days. For subjects with KCCQ score at both baseline and 30 days, the improvement in KCCQ will be calculated as  $KCCQ_{30day} - KCCQ_{baseline}$ . This objective will be evaluated using a Bayesian version of a two-sample t-test (see Section C.11). The posterior probability  $P(H | data)$  will be calculated and compared to a threshold of 0.95.

5. Length of index procedure hospital stay after TAVI vs. SAVR (secondary objective #18). The hypothesis of interest is

$$H: \mu_{TAVI} < \mu_{SAVR}$$

where  $\mu_{TAVI}$  and  $\mu_{SAVR}$  denote the mean length of index hospital stay. This objective will be evaluated using a Bayesian version of a two-sample t-test (see Section C.11). The posterior probability  $P(H | data)$  will be calculated and compared to a threshold of 0.975.

6. Transvalvular mean gradient at 12 months (superiority): TAVI vs. SAVR (secondary objective #12). The hypothesis of interest is

$$H: \mu_{TAVI} < \mu_{SAVR}$$

where  $\mu_{TAVI}$  and  $\mu_{SAVR}$  denote the average mean gradient from at 12 months, measured in mmHg. This objective will be evaluated using a Bayesian version of a two-sample t-test (see Section C.11). The posterior probability  $P(H | data)$  will be calculated and compared to a threshold of 0.975.

7. Effective orifice area at 12 months (superiority): TAVI vs. SAVR (secondary objective #12). The hypothesis of interest is

$$H: \mu_{TAVI} > \mu_{SAVR}$$

where  $\mu_{TAVI}$  and  $\mu_{SAVR}$  denote the mean effective orifice area at 12 months, measured in  $cm^2$ . This objective will be evaluated using a Bayesian version of a two-sample t-test (see Section C.11). The posterior probability  $P(H | data)$  will be calculated and compared to a threshold of 0.975.

8. Change in Kansas City Cardiomyopathy Questionnaire (KCCQ) score from baseline to 30 days (superiority): TAVI vs. SAVR (secondary objective #11). The hypothesis of interest is

$$H: \mu_{TAVI} > \mu_{SAVR}$$

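### Index length of stay (claim 5) is a plain mean over all treated subjects with no visible rule for death before discharge, so an early death counts as a short, favourable stay

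*Combined protocol and SAP*

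**What the plan says.** C.6.8.1 item 18 sets the analysis set: "The length of TAVI or SAVR hospital stay will be summarized for all subjects undergoing a trial procedure". It also sets the method: "The endpoint will be evaluated between groups using a Bayesian version of a t-test". In C.6.10.1, claim 5 tests whether the TAVI mean is below the SAVR mean at a posterior threshold of 0.975; the two parameters "denote the mean length of index hospital stay".

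C.6.10 places this claim in Subfamily #2, described as "Secondary (superiority) objectives #5–#18 as enumerated below, tested in ordered sequence". Testing in that subfamily stops at the first failure, so claim 5 must pass before any of claims 6 to 18 is tested. The error rate is split between the two subfamilies "so that each subfamily is tested using a type I error rate of 0.025". Superiority on the primary endpoint is the other subfamily and runs in parallel: "It is not necessary to “pass” all objectives in one subfamily in order to test the objective(s) in the other subfamily".

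C.6.4.2 counts a procedure as attempted once the subject is in the procedure room and, for example, anesthesia has been given or a line placed. Deaths on the day of the procedure are therefore in the treated set. Nothing in the text supplied excludes a death before discharge, gives it a score or treats it as a competing event. The start and end of the index stay are not defined either.

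**The concern.** A stay can end in two ways, discharge alive or death, and a plain mean treats them alike. A subject who dies on day 1 contributes about one day, the same as an unusually quick recovery. D.2 lists a shorter hospital stay among the potential benefits of TAVI, and a reader of the label would take claim 5 to mean earlier discharge alive. As defined, the endpoint mixes that with early death.

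Two things are at stake. One is the meaning of the labeling claim. The other is the error rate of a test that opens the way to 13 further superiority claims. Days alive out of hospital (claims 9 and 10) does count death against an arm, but it comes after this gate and so cannot protect it.

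**Working it through.** **Inputs.**
- From C.6.5.2: "The sample size for the mITT population is 1600 subjects", allocated 1:1, so about 800 per arm.
- From C.6.5.2: 30-day mortality of 2.8% in the cited surgical series. It stands in here for in-hospital mortality, which the plan does not give by arm.
- The plan gives no mean, SD, power or death timing for length of stay, so there is no figure of its own to reproduce. Assumed: survivor means of 6 to 10 days, SD 5 to 8 days, and deaths on the days stated below.

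**Effect on one arm.** Let L be the mean stay of subjects discharged alive, d the share dying before discharge and D the mean stay of those who die. Then arm mean = (1 - d)L + dD = L + d(D - L). Deaths lower the mean if D < L and raise it if D > L. With d = 0.028:
- L = 6, D = 3: 0.028 x (3 - 6) = -0.08 day.
- L = 10, D = 1: 0.028 x (1 - 10) = -0.25 day.
- L = 6, D = 20: 0.028 x (20 - 6) = +0.39 day.

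**Effect on the comparison.** Shift in TAVI minus SAVR = d_T(D_T - L_T) - d_S(D_S - L_S). With L_T = 6 and L_S = 10:
- 2.8% per arm, TAVI deaths on day 1, SAVR deaths on day 10: -0.14 - 0 = -0.14 day, favouring TAVI.
- The same timing with TAVI deaths doubled to 5.6%: 0.056 x (1 - 6) = -0.28 day.
- 2.8% per arm, TAVI day 1, SAVR day 5: -0.14 + 0.14 = 0.
- 2.8% per arm, day 1 in both: -0.14 + 0.252 = +0.11 day, against TAVI.

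These are scenarios, not bounds.

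**Against a true gap of several days.** SE = SD x sqrt(2/800) = 0.05 x SD, that is 0.25 to 0.40 day. The difference needed to pass 0.975 is about 1.96 x SE = 0.49 to 0.78 day. The assumed 4-day gap gives z = 4/0.40 = 10 to 4/0.25 = 16. A shift of 0.1 to 0.3 day does not alter that result.

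**When survivor stays are equal.** The chance of a false claim is 1 - Phi(1.96 + shift/SE).
- Equal deaths at equal times: shift 0, chance 0.025.
- TAVI 4%, SAVR 2%, day 3, L = 6, SD 8: shift = -0.02 x 3 = -0.06; 1 - Phi(1.96 - 0.15) = 0.035.
- TAVI 4%, SAVR 2%, day 1, L = 10, SD 5: shift = -0.02 x 9 = -0.18; 1 - Phi(1.96 - 0.72) = 0.11.
- The last case with the rates reversed (TAVI 2%, SAVR 4%): shift = +0.18; chance 0.004.

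**The case against.** The case against giving this much weight has five parts.

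- **The gap is inferred from silence.** C.6.5.2 leaves further detail to the SAP, and claim 5 refers its method to a Section C.11 that is not in the text supplied. A death rule may be there. This stands, and the fix allows for it.
- **The sign is not fixed.** A reader might infer that the endpoint favours TAVI by construction. The documents do not support that: they say nothing about when deaths occur in either arm, and day-1 deaths in both arms turn the shift against TAVI. A reader might also infer that every in-hospital death counts as a good stay, but a death after a long admission lengthens the mean. This objection stands in full.
- **The decision would probably not change.** With a gap of several days it would not. The inflated error rates need survivor stays to be nearly equal and early deaths to differ between arms.
- **The hierarchy gives some protection.** Claim 5 is reached only after non-inferiority on 24-month death or disabling stroke and four further non-inferiority tests, and mortality is compared separately among the MACCE components. This limits how far a shorter stay could be claimed alongside worse survival. It does not change what the mean stay measures.
- **Days in hospital is a legitimate quantity.** As resource use it is, and C.6.13.2 collects it as such. A labeling claim of patient benefit is a different use, and there the two ways of leaving hospital should be kept apart.

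**Conclusion.** The point holds in a limited form. With no death rule visible, item 18 and claim 5 credit a death earlier than the arm's typical stay as a favourable result. Under the assumed stays and a base of 2.8% deaths, the net shift in the scenarios examined lies between about -0.28 and +0.11 day and can favour either arm. It is unlikely to change claim 5 if the true gap is several days. If survivor stays were equal and early deaths were 4% on TAVI against 2% on SAVR, the chance of a false claim would rise from 0.025 to between 0.035 and 0.11. All stays, SDs and death timings here are assumptions.

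A reader might take this as a threat to the primary conclusions. It is not: primary non-inferiority comes before claim 5, and primary superiority does not depend on it. What is affected is the meaning of one labeling claim and, when the gap is small, error control for that claim and the gate to claims 6 to 18. It is worth correcting.

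**What to change.** In item 18 and claim 5, state that death before index discharge is an unfavourable outcome. One workable rule scores such a subject at 30 days, or at the actual stay if longer, and keeps the same Bayesian t-test, threshold and testing order. Thirty days fits the window of 30 days or discharge, whichever is longer, that the plan already uses for claims 13 to 16 and 18. Define the start and end of the stay in the same place. As sensitivity analyses, report the raw mean in subjects discharged alive and an analysis of time to discharge alive with death as a competing event. If the full SAP already has a death rule, confirm it and cite it in item 18 instead.

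**Cost.** A few sentences in two places, with no change in sample size. The 30-day score is a convention.
- **Dilution:** with 2.8% deaths per arm and survivor stays of 6 and 10 days, the means become 0.972 x 6 + 0.028 x 30 = 6.67 and 0.972 x 10 + 0.028 x 30 = 10.56. The gap moves from -4.00 to -3.89.
- **Variance:** in an arm with survivor mean 6 and SD 5, the variance becomes 0.972 x 25 + 0.028 x 0.972 x 24^2 = 40.0, so the SD rises to about 6.3. With that SD in both arms, the difference needed to pass rises from 0.49 to about 1.96 x 0.05 x 6.3 = 0.62 day.

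A real gap of several days would still pass easily.
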